- Adults with Decisional Impairment- If checked, please describe below the type and range of decisional impairment and a rationale for why it is necessary to include adults with decisional impairment:
- Other Populations with Potentially Diminished Capacity (i.e., socially, educationally, economically disadvantaged, elderly, terminally ill) - If checked, specify population below and describe what additional safeguards will be in place to protect the rights and welfare of these subjects:

RESPONSE: We have enrolled approximately 25 patients so far. We would prefer to enroll non-english speaking patients. We are aware of the new IRB protocol regarding non English speaking patients' consent. We would like to apply for the "short-form" consent process in order to continue to enroll non-English speaking patients.

- 14)** Explain how the Investigator has access to a population that would allow recruitment of the required number of subjects within the proposed timeframe:

RESPONSE: [name] and [name] both have busy rhinology practices from which to enroll patients.

- 15)** If subjects are recruited from the investigator's patient population or MEE/SERI employees will be recruited, describe what measures are taken to minimize coercion or undue influence:

RESPONSE: The investigators discuss with the patient the voluntary nature of the study, and the fact that the subjects can withdraw at any time from the study. Also it is discussed with the patient that by not enrolling they will not affect their clinical care at all.

SUBJECT SCREENING/RECRUITMENT

- 16)** Describe any screening methods used to determine eligible subjects (i.e., search of medical records or recruitment databases, completion of screening tests, response to interview questions, etc.):

RESPONSE: Patients will be recruited by [name] and [name] in their clinics from patients that are determined to be candidates for endoscopic sinus surgery and have agreed to undergo surgery. The patient will decide to undergo surgery first, and will then be asked to participate in the study. A script to be used for oral invitation in the study is provided in the application packet.

- 17)** Is [protected health information](#) accessed during the screening process? **YES** **NO**

IF YES, specify the information system(s) and the location of the database(s) you will be accessing during the screening process:

RESPONSE: LMR is accessed for patients' clinical information. This is accessed in the MEEI sinus center.

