- 25) Will there be any out-of-pocket costs to subjects and/or expenses likely to be covered by their insurance for participating in the study? YES NO

IF YES, please specify in detail the costs to subjects and/or their insurance (e.g. co-pays):

RESPONSE: The study drug is provided by the pharmacy free of charge. The study medication supplies are charged to the study's cost center by the pharmacy.

- 26) If applicable, how will the cost of reasonably foreseeable medical care in the event of a research-related injury be covered (e.g., sponsor agreement, likely to be covered by insurance, grant, departmental funds)?

RESPONSE: This would be covered by patients' insurance.

RISK

Risk is the probability and magnitude of harm or discomfort anticipated as a result of participation in the research. Any risks of harm to subjects and/or anticipated discomfort(s) that are reasonably foreseeable, even if unlikely, and the safeguards in place to minimize these risks and discomfort(s) must be identified and discussed below. Risks of harm and discomfort may include: physical harm/discomfort, psychological harm/discomfort, legal harm/discomfort, social harm/discomfort, and economic harm.

- 27) Describe any risks of harm to subjects that are reasonably foreseeable, even if unlikely:

These are listed below:

1. amoxicillin/clavulanate arm:
From the FDA monograph
Gastrointestinal

Diarrhea, nausea, vomiting, indigestion, gastritis, stomatitis, glossitis, black “hairy” tongue, mucocutaneous candidiasis, enterocolitis, and hemorrhagic/pseudomembranous colitis. Onset of pseudomembranous colitis symptoms may occur during or after antibiotic treatment

Hypersensitivity Reactions

Skin rashes, pruritus, urticaria, angioedema, serum sickness–like reactions (urticaria or skin rash accompanied by arthritis, arthralgia, myalgia, and frequently fever), erythema multiforme (rarely Stevens-Johnson syndrome), acute generalized exanthematous pustulosis, and an occasional case of exfoliative dermatitis (including toxic epidermal necrolysis) have been reported. These reactions may be controlled with antihistamines and, if necessary, systemic corticosteroids. Whenever such reactions occur, the drug should be discontinued, unless the opinion of the physician dictates otherwise. Serious and occasional fatal hypersensitivity (anaphylactic) reactions can occur with oral penicillin.

Liver

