A moderate rise in AST (SGOT) and/or ALT (SGPT) has been noted in patients treated with ampicillin-class antibiotics but the significance of these findings is unknown. Hepatic dysfunction, including increases in serum transaminases (AST and/or ALT), serum bilirubin, and/or alkaline phosphatase, has been infrequently reported with Augmentin. It has been reported more commonly in the elderly, in males, or in patients on prolonged treatment. The histologic findings on liver biopsy have consisted of predominantly cholestatic, hepatocellular, or mixed cholestatic-hepatocellular changes. The onset of signs/symptoms of hepatic dysfunction may occur during or several weeks after therapy has been discontinued. The hepatic dysfunction, which may be severe, is usually reversible. On rare occasions, deaths have been reported (less than 1 death reported per estimated 4 million prescriptions worldwide). These have generally been cases associated with serious underlying diseases or concomitant medications.

Renal

Interstitial nephritis and hematuria have been reported rarely. Crystalluria has also been reported

Hemic and Lymphatic Systems

Anemia, including hemolytic anemia, thrombocytopenia, thrombocytopenic purpura, eosinophilia, leukopenia, and agranulocytosis have been reported during therapy with penicillins. These reactions are usually reversible on discontinuation of therapy and are believed to be hypersensitivity phenomena. A slight thrombocytosis was noted in less than 1% of the patients treated with Augmentin. There have been reports of increased prothrombin time in patients receiving Augmentin and anticoagulant therapy concomitantly.

Central Nervous System

Agitation, anxiety, behavioral changes, confusion, convulsions, dizziness, insomnia, and reversible hyperactivity have been reported rarely.

Miscellaneous

Tooth discoloration (brown, yellow, or gray staining) has been rarely reported. Most reports occurred in pediatric patients. Discoloration was reduced or eliminated with brushing or dental cleaning in most cases.

2. Placebo Arm:

The main theoretical risk from not giving antibiotics post operatively would be a risk of postoperative infection. This would manifest as sinusitis-like symptoms. Worst case scenario would result in complications of sinusitis (orbital infection, meningitis, brain abscess). These complications are rare, and [name] has not experienced them while not giving routine postoperative antibiotics as is his usual practice.

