- 34) Are there any potential direct benefits to individual subjects related to the research?
 YES NO

IF YES, please explain (address whether these benefits (e.g., clinical, therapeutic) would be available to subjects outside of the research):

RESPONSE:

- 35) Explain the potential benefits to science, and/or society (indirect benefits) which may accrue as a result of this research:

RESPONSE: Antibiotic resistance is growing in the world, and this study may provide prospective, randomized data that antibiotics do not result in a benefit to patients. Hopefully surgeons would stop giving postoperative antibiotics, and decrease the risk of side-effects from antibiotics (allergic reactions, clostridium difficile infection, GI upset, etc) to future patients. Also health care costs would be decreased by reducing antibiotic prescriptions.

- 36) If more than minimal risk, address how risks relate to benefits:

RESPONSE: While not “minimal risk”, the risk to patients is low, as detailed above. Many patients have adverse reactions to antibiotics, and if this study shows that the outcomes of patients undergoing sinus surgery without antibiotics are not worse, then hopefully less patients will be prescribed antibiotics.

CONSENT PROCESS

- 37) Describe the consent process in detail. Include who specifically will be obtaining consent, describe their knowledge/experience in obtaining consent from research subjects, and include the location where study information will be exchanged, how (consent form, orally, information sheet, etc.) information is being conveyed to subjects, and when the consent will be obtained (e.g. during pre-surgical visit, about one week before the screening visit):

RESPONSE: Consent will be obtained by [name], [name] or [name] in the clinic during the subject's preoperative visit in the MEEI sinus center. There is a formal consent form that is signed by patients and an oral script (these are on IRBNET). Subjects can think about the study and opt out of randomization at the time of surgery (usually 2-4 weeks elapse between preoperative visit and surgery).

- 38) Indicate which of the following consent procedures you are contemplating for this research:

Written consent form

- Short form process (only appropriate for minimal risk studies)
** If checked, answer question 42 below.*
- Assent from adults with diminished decision-making capacity
**If checked, provide justification below:*
- Assent from children and parental permission

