- Oral consent or implied consent (e.g. completing a survey)
**If checked, provide justification based on [45 CFR 46.117\(c\)](#) below:*
- Requesting a waiver of informed consent from the HSC
**If checked, provide justification based on [45 CFR 46.116\(c\) and \(d\)](#) below:*

RESPONSE:

- 39)** Describe any foreseeable circumstances and/or reasons under which the subject's participation in the research may be terminated:

RESPONSE: If the patient does not want to participate further then they may opt out at any time during the study.

- 40)** How is subject comprehension assessed initially and throughout the consent process? Is the manner in which information is presented appropriate for the population? In cases where subject comprehension is severely limited what special provisions have been made (is there a third party involved in the consent process)? Discuss below:

RESPONSE: The investigators will describe the study according to the oral script and ask the patient if they understand everything that has been explained to them. We will ask them if they have any questions and answer them to their satisfaction. If the patients' comprehension is severely limited then we will not include them in the study.

- 41)** If the research-related intervention or interaction will occur on the same day that the subject initially receives information about the study, justify why this is appropriate/necessary:

RESPONSE: It will not be on the same day, patients will be enrolled at their post operative visit.

- 42)** Describe additional provisions in place for non-English speaking subjects (view [guidance](#)), including the availability/presence of translators (fluent in both English and the subject's spoken language) during the consent process and the translation of consent documents in a language understandable to them (when consent documents are translated all translated versions must be accompanied by an attestation from the translator) **OR** justify why non-English speaking subject are being excluded from the research:

RESPONSE: We would like to apply for use of the short form consent process for patients that do not speak English. We have used translators for patients that are not English speakers previously.

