### **Statistical Analysis Plan**

The primary endpoint was the overall change in SNOT-22 scores from baseline to the final study visit. Secondary outcomes included the change in LK Endoscopic Score from the same time points, as well as rates of post-operative infection. Additional exploratory analyses included the effect of baseline clinical factors, including baseline sinus culture results, history of prior sinus surgery, comorbid asthma, and presence of nasal polyps.

The primary outcome and secondary outcome were analyzed using a repeated-measures analysis of variance (ANOVA) to assess for a group x time interaction on clinical scores. For the secondary analysis of the primary outcome, this model was modified to include baseline clinical covariates in a repeated-measures analysis of covariance (ANCOVA).

The achieved power for non-inferiority was calculated via the same methods as the prospective power analysis. Rather than an *a priori* estimate of standard deviation in scores, the achieved power was based on the actual number of randomized subjects and the actual pooled standard deviation of post-treatment SNOT-22 scores in the two groups. The non-inferiority margin was 9 units on the SNOT-22.

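### The SAP names a repeated-measures ANOVA but no analysis set and no rule for missing final scores; run on complete cases, it could bias the non-inferiority comparison, in a direction the documents do not settle

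*SAP*

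**What the plan says.** The SAP's first paragraph defines the outcome: "The primary endpoint was the overall change in SNOT-22 scores from baseline to the final study visit". The change in LK endoscopic score over the same interval is a secondary outcome, as is the post-operative infection rate. The second paragraph gives the method: "The primary outcome and secondary outcome were analyzed using a repeated-measures analysis of variance (ANOVA"), testing a group-by-time interaction. The third gives the criterion: "The non-inferiority margin was 9 units on the SNOT-22". The supplied SAP text contains no analysis population, no handling of missing final scores, no table of withdrawals and no sensitivity analysis.

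On leaving the study, the protocol's answer to Q39 (ending of participation) is: "If the patient does not want to participate further then they may opt out at any time during the study". Q15 likewise says that patients are told of "the fact that the subjects can withdraw at any time from the study". Neither answer says whether scores are sought after a patient stops study drug or leaves.

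**The concern.** A patient with no final SNOT-22 has no observed primary outcome. A classical repeated-measures ANOVA needs every score in the model for each subject, so unless the SAP says otherwise it compares completers only. That is unbiased only if the losses do not distort the difference between arms.

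The protocol gives grounds to doubt this. Q27 names post-operative infection as the main theoretical risk on placebo and adds: "This would manifest as sinusitis-like symptoms". Those symptoms are what a sinusitis quality-of-life score responds to. On antibiotic, Q27 lists drug reactions. Loss could therefore depend on both arm and outcome.

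The stake is a conclusion, stated as the study's hope in Q36, that patients do no worse without antibiotics. If placebo patients who do badly are lost selectively, the completers' difference shrinks, and in a non-inferiority comparison that is the anti-conservative direction.

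**Working it through.** **The plan's own figures.** The documents give no dropout rate and no bias figure to reproduce. Protocol Q11 gives a total of 140. The supplied text gives no alpha, power, SD or allocation ratio, so 140 can be neither confirmed nor contradicted. Assuming 1:1 allocation (70 per arm), true difference 0, one-sided 0.025 and 80% power, a 9-unit margin implies SD = 9 × √35 / (1.960 + 0.842) = 19.0. Other combinations also fit: SD 16.4 at 90% power, or 21.4 at one-sided 0.05 with 80% power. I use SD 19 and show 16 to 22.

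**Bias of a completers-only difference.** Let d be the share of an arm without a final score, and D how much worse those patients would have scored than that arm's completers (P placebo, A antibiotic). The full-arm mean is worse than the completers' mean by d × D. The bias toward non-inferiority is therefore

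bias = dP × DP − dA × DA.

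It favours non-inferiority only when the placebo term is the larger.

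**False non-inferiority rate** at a true placebo deficit of exactly 9:

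rate = Φ(bias / SE − 1.960), with SE = SD × √[1/(70(1 − dP)) + 1/(70(1 − dA))].

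Worked case: dP = 10%, DP = 20, no antibiotic loss.
- Bias = 0.10 × 20 = 2.0.
- SE = 19 × √(1/63 + 1/70) = 3.30.
- Rate = Φ(0.606 − 1.960) = Φ(−1.354) = 8.8%.

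| Placebo loss (D) | Antibiotic loss (D) | Bias, points | Rate at SD 19 | SD 22 to SD 16 |
|---|---|---|---|---|
| none | none | 0 | 2.5% | 2.5% |
| 5% (20) | none | 1.0 | 4.9% | 4.5% to 5.5% |
| 10% (20) | none | 2.0 | 8.8% | 7.5% to 10.8% |
| 20% (20) | none | 4.0 | 21.6% | 17.2% to 28.6% |
| 10% (20) | 10% (20) | 0 | 2.5% | 2.5% |
| 10% (10) | 10% (20) | −1.0 | 1.2% | 1.3% to 1.0% |

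Every d and D is an assumption. The last two rows matter as much as the others: equal losses cancel, and worse losses on antibiotic make the analysis conservative. A bias equal to the whole margin needs an extreme case, such as 30% placebo-only loss with leavers 30 points worse (0.30 × 30 = 9).

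**The case against.** Much of the opposing case stands.

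- **Deletion of incomplete cases is inferred.** The SAP does not say that patients without a final score are dropped; this follows from the method's name in its classical form. The SAP bases achieved power on the number randomized, which might suggest an all-randomized analysis, but that sentence concerns power only.
- **A reader might infer that the bias is established and runs toward non-inferiority.** The documents do not support that. They record no amount, arm or reason of dropout, and drug reactions on antibiotic are a competing source of loss.
- **A reader might infer a conflict between Q27 and Q39.** There is none. The Q27 sentence, "Whenever such reactions occur, the drug should be discontinued, unless the opinion of the physician dictates otherwise", is text from the drug's monograph about stopping a drug. Q39 is about leaving the study. Read on its face, Q39 does not make a reaction or a treated infection end participation.
- **A reader might infer that half the margin can be hidden.** If failing patients score 30 points worse, and 20% fail on placebo against 5% on antibiotic, the true difference is 30 × 0.15 = 4.5; it disappears if every failing patient leaves. None of these inputs is in the documents, and 4.5 lies inside the margin, so non-inferiority would still be the correct conclusion.
- **Some failures are caught elsewhere.** All patients have an endoscopic visit at one week (Q32), and infection rate is a secondary outcome. Neither supplies a final SNOT-22.
- **Some exits are harmless.** Q37 says "Subjects can think about the study and opt out of randomization at the time of surgery". Leaving before randomization does not bias the randomized comparison.
- **Material is missing from the supplied text.** Consent pages were removed and the prospective power analysis is not included, so silence on follow-up after withdrawal is weak evidence.

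What remains is the gap in the SAP itself: a method that in its usual form needs complete data, with no stated analysis set or missing-score rule, supporting a non-inferiority claim.

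**Conclusion.** The point holds in conditional form and should be acted on. As written, the SAP leaves open a complete-case comparison of SNOT-22 and LK change, and gives no means of judging whether missing scores could have produced a non-inferiority result. The bias could be toward that result, absent or against it.

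The illustration shows only that a modest imbalance would matter: 2 points, well under the 9-unit margin, takes the error rate from 2.5% to about 9%. That rests on assumed values of 70 per arm, SD 19, one-sided 0.025, a true deficit at the margin, and 10% placebo-only loss with leavers 20 points worse. It is not an estimate of what happened in this trial.

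**What to change.** In the SAP:

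1. Define the analysis set for SNOT-22 and LK as all randomized patients, as assigned. Replace the repeated-measures ANOVA with a likelihood-based mixed model for repeated measures that uses every available score, and report the between-arm difference in change at the final visit with its confidence interval.
2. Tabulate missing final scores by arm and reason.
3. Add a tipping-point analysis for SNOT-22: worsen the missing placebo final scores step by step until the confidence limit reaches 9, and report how large that shift is. This step is essential. The mixed model assumes data missing at random, gains little for patients with only a baseline score, and does not by itself cure outcome-dependent loss.

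The SAP is written in the past tense. If the analysis is already done, report all three as post hoc. If follow-up is still open, add to the protocol that stopping study drug is not withdrawal from the study and that scores are still collected at the scheduled visits; this leaves untouched any rule on when drug is stopped. I do not propose telephone or mailed questionnaires, because Q50 leaves telephone, address and email unchecked among the identifiers to be obtained.

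Cost: some SAP wording, slightly more analysis work, and some scores collected off drug.

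### The SAP sets a 9-unit SNOT-22 non-inferiority margin, but its only stated primary test is for a difference, and nothing is compared with the margin

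*SAP*

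**What the plan says.** The aim is a not-worse conclusion. Protocol question 36 (risks in relation to benefits) ties the value of the trial to what follows "if this study shows that the outcomes of patients undergoing sinus surgery without antibiotics are not worse".

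The SAP (Statistical Analysis Plan) then says:

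- Paragraph 1, endpoint: "The primary endpoint was the overall change in SNOT-22 scores from baseline to the final study visit".
- Paragraph 2, test: the primary and secondary outcomes were "analyzed using a repeated-measures analysis of variance (ANOVA) to assess for a group x time interaction on clinical scores". A secondary analysis adds baseline covariates to the same model and does not mention the margin.
- Paragraph 3, non-inferiority: "The achieved power for non-inferiority was calculated via the same methods as the prospective power analysis". For this, "the achieved power was based on the actual number of randomized subjects and the actual pooled standard deviation of post-treatment SNOT-22 scores".
- Paragraph 3, margin: "The non-inferiority margin was 9 units on the SNOT-22".

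The supplied text contains no non-inferiority hypothesis, alpha level, sidedness or confidence interval, and no rule that sets the estimated difference against 9.

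**The concern.** A group-by-time interaction test asks whether the arms differ. Failing to reject its null hypothesis does not show that placebo is worse by less than 9. A wide confidence interval can include both zero and a deficit beyond 9, and the less precise the trial, the easier it is to be non-significant.

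The achieved-power figure does not fill the gap. Its inputs are the number randomised, the pooled post-treatment SD and the margin. The observed difference is not among them, so the figure is the same whether placebo looks better or clearly worse. It also uses the SD of post-treatment scores, while the endpoint is a change score.

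The plan does not say how a non-significant interaction would be interpreted. At stake is a claim that antibiotics can safely be omitted, resting on a non-significant p-value and a reassuring power figure when the data have not excluded a deficit beyond the plan's own margin.

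**Working it through.** **Inputs from the documents.** Margin 9 (SAP, paragraph 3). Planned enrolment 140 (protocol, question 11).

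**Assumptions.** 1:1 allocation, so n = 70 per arm (140 is planned enrolment, not the number analysed). Two time points, so the interaction equals the between-group difference in change. Two-sided 0.05 for the interaction and a two-sided 95% CI for non-inferiority. The documents give no SD, so the SD of change is varied. Positive differences mean placebo is worse.

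**The plan's own figure.** 140 cannot be reproduced, because the SD, alpha, power and dropout behind it are not in the supplied text. Working backwards by normal approximation with true difference 0 and no dropout, SD = 9 × √(70/2) / (z for 1−α + z for power). This gives 19.0 at one-sided 0.025 and 80% power, 16.4 at 0.025 and 90%, 21.4 at 0.05 and 80%, and 18.2 at 0.05 and 90%. This neither confirms nor refutes 140.

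**Step 1: where the two readings disagree.** SE = SD × √(2/70). The critical t on 138 degrees of freedom is 1.977, and the half-width is h = 1.977 × SE. The interaction is non-significant if the observed difference lies within ±h. Non-inferiority needs an observed difference below 9 − h. Deficits between 9 − h and h are therefore non-significant yet fail non-inferiority.

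**Step 2: how often a true deficit of 9 is non-significant.** This is P(|t| < 1.977) for a noncentral t with noncentrality 9/SE. Under the confidence-limit rule the corresponding false-claim rate is 2.5%.

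| SD of change | h | 9 − h | Non-significant but fails the margin | P(non-significant), true deficit 9 |
|---|---|---|---|---|
| 10 | 3.34 | 5.66 | none | under 0.1% |
| 12 | 4.01 | 4.99 | none | 0.7% |
| 13 | 4.35 | 4.65 | none | 1.8% |
| 15 | 5.01 | 3.99 | 4.0 to 5.0 | 5.9% |
| 18 | 6.02 | 2.98 | 3.0 to 6.0 | 16.4% |
| 20 | 6.68 | 2.32 | 2.3 to 6.7 | 24.7% |
| 25 | 8.36 | 0.64 | 0.6 to 8.4 | 43.8% |

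The zone vanishes when h = 4.5, that is at SD = 4.5 / (1.977 × √(2/70)) = 13.5. With 60 per arm the last column is 9.7%, 22.5%, 31.4% and 50.2% at SD 15, 18, 20 and 25.

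**Step 3: one result worked through.** Let the baseline, post-treatment and change SDs all be 18, so SE = 18 × √(2/70) = 3.04. An observed deficit of 5 gives t = 5/3.04 = 1.64, p = 0.10, and a 95% CI of 5 ± 6.02, or −1.0 to 11.0. Achieved power at one-sided 0.025 is 84%. The p-value and the power figure both look reassuring, but the interval crosses 9. With an observed deficit of 0, achieved power would still be 84%, while the upper limit would be 6.0 and the margin would be met.

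**Step 4: does a power screen rescue the plan?** Suppose not worse were claimed only when the interaction is non-significant and achieved power is at least 80%, a threshold the SAP does not state. Simulation at a true deficit of 9 (40,000 trials in each of nine scenarios, SDs 15 to 25, baseline-to-post correlation 0.4 to 0.7) gives false-claim rates of about 0 to 23% with power computed at one-sided 0.025, and about 0 to 28% at 0.05. The confidence-limit rule gave 2.4 to 2.6% in all nine.

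**The case against.** Several points can be made for the plan.

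- **The SAP never says that non-significance will be read as non-inferiority.** This stands. The percentages in Step 2 describe a possible misreading, not the error rate of a written rule. But the plan offers no other route from the data to a not-worse conclusion.
- **A prospective power analysis existed and is not in the supplied text.** It may give an alpha and sidedness, and its absence is not counted as an error. However, the SAP cites it only as the method for computing achieved power, not as a test of the result.
- **The size depends on the SD.** This stands. At 70 per arm the problem disappears below an SD of change of about 13.5, and a high baseline-to-final correlation lowers that SD.
- **The 95% level is a reviewer's choice.** This stands. With a 90% CI the lower ends of the discordant zones rise to 4.8, 4.0, 3.4 and 2.0 at SD 15, 18, 20 and 25. The zones narrow but remain.
- **Question 36 is a conditional remark, not a formal hypothesis.** True, but the SAP itself sets a non-inferiority margin, so the intention does not rest on that sentence.

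**Conclusion.** The concern holds, and the plan should not stand as written. It states a margin of 9 but has no test against it. Followed literally, it yields an interaction p-value and a power figure, and neither can support a conclusion that omitting antibiotics is not worse. This follows from the text and needs no assumption about the SD.

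The size is illustrative. It rests on 70 per arm, two time points, a two-sided 0.05 interaction test and an assumed SD of change. A true deficit equal to the margin would go undetected by the interaction test in about 6% to 44% of trials for SDs of 15 to 25, and in fewer than 2.5% for SDs of 13 or less. The planned model is usable; what is missing is the decision rule.

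**What to change.** From the planned repeated-measures model, estimate the placebo-minus-antibiotic difference in SNOT-22 change from baseline to the final visit as a single contrast, with a two-sided 95% CI. Conclude non-inferiority only if the upper limit, in the direction of placebo being worse, is below 9. State the confidence level explicitly; 95% is proposed here because the supplied text gives none. Report the interaction p-value and the achieved power as descriptive only. A single contrast also keeps the answer on the stated endpoint if the model includes more than two visits, where the interaction becomes an omnibus test.

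The cost is a few lines of SAP wording and one contrast from a model already planned, with no extra patients or visits. There are two downsides. The conclusion may be less favourable than a report of no significant difference. And the SAP is written in the past tense: if the results were already known when the rule is added, it must be labelled post hoc, although the contrast can still be computed and reported against the stated margin.
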